Upon sponsor discretion, this study was terminated before the study completed enrollment; however, all planned analyses will still occur. Sixty-five (65) subjects were enrolled in the study before termination. The statistical plan described hereafter is an *a priori* plan. It will be submitted to file prior to any unblinded inferential or descriptive analysis of data pertaining to Mayne Pharma's study 18-ICH-001.

2. Study Objectives and Endpoints

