4.1. Introduction

Data processing, tabulation of descriptive statistics, calculation of inferential statistics, and graphical representations will be performed primarily using SAS (release 9.4 or higher). If the use of other software is warranted, the final statistical methodology report will detail what software was used for what purposes.

Continuous (quantitative) variable summaries will include the number of subjects (n) with nonmissing values, mean, standard deviation (SD), standard error (SE), median, minimum, and maximum.

Categorical (qualitative) variable summaries will include the frequency and percentage of subjects who are in the particular category or each possible value. In general, the denominator for the percentage calculation will be based upon the total number of subjects in the study population for the treatment groups, unless otherwise specified. The denominator for by-visit displays will be the number of subjects in the relevant study population with nonmissing data at each study visit.

The minimum and maximum will be reported with the same degree of precision (i.e., the same number of decimal places) as the observed data. Measures of location (mean and median) will be reported to 1 degree of precision more than the observed data and measures of spread (SD, SE) will be reported to 2 degrees of precision more than the observed data.

Percentages will be presented to 1 decimal place, unless otherwise specified and with the following exceptions: a percentage of 0% will not be displayed (i.e., only the count of 0 will be displayed), and a percentage of 100% will be displayed with 0 decimal places.

Unless otherwise indicated, all statistical tests will be conducted at the 0.05 significance level using 2-tailed tests, and *P* values will be reported. Corresponding 95% confidence intervals (CIs) will be presented for statistical tests. A *P* value of ≤ 0.10 but > 0.05 will be considered evidence of a trend.

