7.4. Exposure and Compliance

Compliance by tube weight and compliance by number of doses will be summarized by treatment group using descriptive statistics. The total weight of tubes dispensed and returned, as well as total number of tubes dispensed, returned, and returned unused will also be summarized. This analysis will be conducted for the Safety population and for the OLE Safety population.

A subject is compliant with study product if he or she takes at least 80%-120% of the scheduled doses as assessed by number of doses taken reported, supplemented by tube weight and diary entries. The number and percentage of subjects who were compliant will be tabulated by treatment group for the Double-blind Period and overall for the OLE. Derivations of compliance are defined in Section 6.1.7.

All initial study drug application, drug accountability (dispensed and returned), and subject diary data collected will be listed. Changes in treatment administration or treatment dispensation due to COVID-19 including start and end dates of change, method of alternative administration/dispensation, dosing interruptions, and relevant changes to compliance expectations (weights or tube counts) will be documented from the COVID-19 visit impact log.

8. Efficacy Analysis

All efficacy endpoints will be summarized using the ITT population. The primary analysis will be repeated in the mITT and PP populations.

Summaries of efficacy variables in the OLE will be provided using the OLE ITT. Primary IGA summaries will also be provided for the OLE mITT and OLE PP populations. For continuous efficacy analyses using MMRM, only formal comparisons of change from baseline will be performed in the OLE. No other formal inferential analyses will be conducted for efficacy variables in the OLE.

All efficacy data, regardless of population, will be presented in data listings.

If alternative methods are used for capturing efficacy assessments (i.e., in person not on site at the subject's home, remotely with visual aid, or remotely via telephone), additional sensitivity or subgroup analyses may be performed to assess the potential impact to efficacy analyses. These will be delineated as ad hoc analyses in the CSR.

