The change from baseline IGA score will be analyzed using a mixed model for repeated measures (MMRM). The MMRM model will include change from baseline in IGA score as the dependent variable, treatment, study visit, treatment-by-visit interaction, and age group as fixed effects, subject as a random effect, and baseline IGA score as a covariate. All post-baseline study visits will be included in the model; however, the primary comparison will be between the active trifarotene cream HE1 groups and vehicle at Day 90. An unstructured covariance matrix will be used to model the within-subject errors. The Kenward-Roger approximation will be used to estimate degrees of freedom. In case of convergence issues, other covariance structures will be explored including autoregressive (AR(1)), compound symmetry (CS), and variance components (VC) with each model fit to find the covariance structure with the best fit. The fit statistics will be compared for all covariance structures; the structure with the smallest Akaike information criterion will be retained as the preferred model and noted in the resulting table. For the OLE period, the model will not include treatment or treatment-by-visit interaction since all subjects receive the same treatment in the OLE.

The least squares (LS) mean change from baseline will be presented along with the associated 95% CI within each treatment group. The overall *P* value of the model will be presented to test

the null hypothesis that the change from baseline to subsequent study visit is 0 with a 2-sided alternative considering a difference in either direction.

In comparing treatments (active trifarotene cream HE1 groups minus vehicle), LS mean differences in change from baseline will be presented along with associated 95% CIs and *P* values. The null hypothesis that the difference in change from baseline in active trifarotene cream HE1 groups minus control vehicle is 0 with a 2-sided alternative considering a difference in either direction. Even if a difference from vehicle is observed, as described above, successful treatment is defined as clear/almost clear overall (IGA scores of 0 or 1) and at least a 2-grade change from baseline.

The observed value and change from baseline in IGA score will also be summarized descriptively by study visit and treatment group using descriptive statistics in addition to the above noted models for the Double-blind Period and OLE. Categorical IGA scores will also be presented.

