8.2. Secondary Efficacy Analyses

8.2.1. Visual Index for Ichthyosis Severity (VIIS)

The investigator will rate the subject's condition using the 5-point VIIS for each body area (chest/abdomen, back, legs, and arms) and an overall score at all clinic visits. The scoring is as follows in [Table 5](#).

Table 5: VIIS Scoring Definitions

Score	Definition
0	Normal skin; no perceptible scale, or smoothening
1	Areas of normal skin intermixed with areas showing smoothening (diminished fine skin markings; shininess; waxiness) or small scales (visible separated/fractured stratum corneum)
2	Confluent smoothening (diminished fine skin markings; shininess; waxiness) or small scales (visible separated/fractured stratum corneum)
3	Confluent scales (visibly separated/fractured stratum corneum) including some large (>1cm), thick scales
4	Confluent, primarily large, thick scales

The change from baseline VIIS score will be analyzed using an MMRM. The MMRM model will include change from baseline in VIIS score as the dependent variable, treatment, study visit, treatment-by-visit interaction, and age group as fixed effects, subject as a random effect, and baseline VIIS score as a covariate. All post-baseline study visits will be included in the model; however, the primary comparison will be between the active trifarotene cream HE1 groups and vehicle at Day 90. An unstructured covariance matrix will be used to model the within-subject errors. The Kenward-Roger approximation will be used to estimate degrees of freedom. In case of convergence issues, other covariance structures will be explored including AR(1), CS, and VC with each model fit to find the covariance structure with the best fit. The fit statistics will be compared for all covariance structures; the structure with the smallest Akaike information criterion will be retained as the preferred model and noted in the resulting table. For the OLE period, the model will not include treatment or treatment-by-visit interaction since all subjects receive the same treatment in the OLE.

The LS mean change from baseline will be presented along with the associated 95% CI within each treatment group. The overall *P* value of the model will be presented to test the null hypothesis that the change from baseline to subsequent study visit is 0 with a 2-sided alternative considering a difference in either direction.

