Update footnote [2] to read “Number of subjects with a 50% reduction in IGA score from baseline at a visit. Baseline is defined as the last non-missing assessment recorded prior to the first dose of treatment in the Double-blind Period. Higher IGA scores represent more severe disease.”

Update [3] to read “Estimates for odds ratio, 95% CI for odds ratio, and P value are from a logistic regression model with treatment, baseline IGA score, and age group as factors. The odds ratio is the estimate of the odds of having a 50% reduction in IGA score from baseline for subjects treated with Trifarotene cream HE1 relative to that for subjects treated with vehicle. Age group is defined as adolescents (ages 12 to 17 years, inclusive) and adults ≥ 18 years.”

Table 14.2.1.5.2
Proportion of Subjects with a 50% Reduction in IGA score from Baseline
OLE ITT Population

Same shell as Table 14.2.1.1.2

Programming note: Update “Successful Resolution [2]” row text to read “50% Reduction from Baseline [2]”.

Update Note: to read “Note: Percentages are $n/\text{Number of subjects in the OLE ITT population within treatment group} \times 100$. All subjects received Trifarotene cream HE1 200 ug/g in the OLE.”

Update footnote [2] to read “Number of subjects with a 50% reduction in IGA score from baseline at a visit. Baseline is defined as the last non-missing assessment recorded prior to the first dose of treatment in the Double-blind Period. Higher IGA scores represent more severe disease.”

Table 14.2.1.6.1
MMRM Analysis of Change from Baseline in IGA Score
ITT Population

Study Visit Statistic [1]	Trifarotene cream HE1 100 ug/g (N=XXX)		Trifarotene cream HE1 200 ug/g (N=XXX)	
	Observed	CFB	Observed	CFB
Baseline [2]				
n	XXX		XXX	
Mean (SD)	XX.XX (XX.XXX)		XX.XX (XX.XXX)	
Median	XX.XX		XX.XX	
Min, Max	XX.X, XX.X		XX.X, XX.X	
Day 14				
n	XXX	XXX	XXX	XXX
Mean (SD)	XX.XX (XX.XXX)	XX.XX (XX.XXX)	XX.XX (XX.XXX)	XX.XX (XX.XXX)
Median	XX.XX	XX.XX	XX.XX	XX.XX
Min, Max	XX.X, XX.X	XX.X, XX.X	XX.X, XX.X	XX.X, XX.X
LS Mean (SE) CFB		X.XX (X.XXX)		X.XX (X.XXX)
95% CI for LS Mean CFB		(X.XX, X.XX)		(X.XX, X.XX)
P value for CFB = 0		X.XXXX		X.XXXX
Comparison vs. Vehicle				
Difference in LS Mean (SE)		X.XX (X.XXX)		X.XX (X.XXX)
95% CI for Difference in LS Mean		(X.XX, X.XX)		(X.XX, X.XX)
P value for Difference		X.XXXX		X.XXXX

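### Five MMRM sections assign the null of zero change from baseline to an overall model P value that does not test it; the table shell implies the right test, so text and shell must be aligned

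*SAP*

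**What the plan says.** Section 8.2.1 (VIIS) fits an MMRM to change from baseline with "treatment, study visit, treatment-by-visit interaction, and age group as fixed effects, subject as a random effect, and baseline VIIS score as a covariate", and "An unstructured covariance matrix will be used to model the within-subject errors". It presents the LS mean change with a 95% CI in each arm, and then names a single model-wide P as the within-group test: "value of the model will be presented to test the null hypothesis that the change from baseline to subsequent study visit is 0", two-sided. The same sentence is used in Section 8.1.1 for the IGA (the overall P "value of the model will be presented to test" the same null) and in Sections 8.2.2, 8.2.3 and 8.2.4. The DLQI/cDLQI model differs only in having no age-group term.

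The shell of Table 14.2.1.6.1 treats the same hypothesis differently. Under each arm's LS mean change and its 95% CI, at each visit, there is a row "P value for CFB = 0". Footnote [1] takes the LS means, CIs and P values from the MMRM. The tables for the other four endpoints reuse this shell, and no planned table has a row for an overall model P value.

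For the open-label extension (OLE), the opening of Section 8 says that for the MMRM endpoints "only formal comparisons of change from baseline will be performed in the OLE". The OLE models drop treatment and its interaction with visit. The general rule in Section 4.1 is that "all statistical tests will be conducted at the 0.05 significance level using 2-tailed tests".

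**The concern.** The dependent variable is already a change score, so the stated null concerns the level of an arm's mean at a visit. An overall model P value concerns something else: whether the covariates explain variation in the change scores, or whether the repeated scores are correlated. Neither asks whether the mean is zero.

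The SAP thus names two different tests for one hypothesis. One overall P value cannot fill a row that needs a value for every arm and visit. A programmer or report author who follows Section 8 would print, beside the CI for an LS mean, a P value for another hypothesis. The CI could exclude 0 while P is large, or the reverse. In the OLE no vehicle comparison is left to fall back on, so the within-group test carries all the formal efficacy inference for IGA, VIIS, roughness and palm/sole.

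**Working it through.** The SAP gives no figure to reproduce. The check is to write out what each candidate P value tests and then see how it behaves.

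**Inputs from the SAP.** Model terms and unstructured covariance (Section 8.2.1); four post-baseline double-blind visits (Days 14, 30, 60, 90); three arms at 1:1:1; two-sided 5% level; and sample size, since "Sixty-five (65) subjects were enrolled in the study before termination" (Section 1).

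**Assumptions, not in the SAP.** Normal scores with equal SD at all visits, 25% adolescents, no missing data, and baseline/follow-up correlation r between 0.5 and 0.9.

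**Step 1: the parameters.** With baseline centred:

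LS mean (arm k, visit v) = intercept + treatment_k + visit_v + interaction_kv + age term.

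Non-intercept coefficients: 2 (treatment) + 3 (visit) + 6 (interaction) + 1 (baseline) + 1 (age) = 13. The null of zero change is that the LS mean is 0, and this includes the intercept.

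**Step 2: what each candidate tests.**
- *Joint fixed-effects test (13 df):* all 13 coefficients are 0. If every arm changes by the same amount d at every visit, only the intercept moves, so the test cannot see d.
- *Null-model likelihood-ratio test:* unstructured against independent equal-variance errors, 4×5/2 − 1 = 9 df. It says nothing about means.
- *Single F tests* of treatment, visit or interaction: differences between arms or visits. These are also blind to a common d.

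**Step 3: why the joint test can reject with no mean change.** With equal SDs the slope of change on baseline is r − 1: −0.5, −0.3 and −0.15 for r = 0.5, 0.7 and 0.85. With correlation ρ between follow-up visits, the slope alone contributes the noncentrality

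λ = n(1 − r)² × 4 / [(1 − ρ) + 4(ρ − r²)].

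For n = 65, r = 0.7, ρ = 0.8: λ = 65 × 0.09 × 4/1.44 = 16.25. Against a chi-square on 13 df (critical value 22.36) this gives 75% rejection.

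**Step 4: simulated rejection rates, N=65, true mean change 0 everywhere.**

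| r (ρ) | Joint test | Covariance LRT | LS mean t test |
|---|---|---|---|
| 0.5 (0.5) | 98% | 98% | about 5–6% |
| 0.7 (0.7) | 81% | 100% | about 5–6% |
| 0.9 (0.9) | 25% | 100% | about 5–6% |
| 0.5 (0.7) | 95.2% | 100% | 5.8% |
| 0.7 (0.8) | 71.2% | 100% | 5.9% |
| 0.85 (0.9) | 31.6% | 100% | 5.5% |

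The first three rows use 800 replicates each and the last three use 2000. The LS mean test is for one arm at the last visit. The formula in Step 3 gives 99.8%, 86%, 27%, 98%, 75% and 35% for the six rows. That is the same pattern, slightly higher because it treats the covariance as known. In the last three rows the single treatment, visit and interaction F tests reject 4.6% to 6.2%.

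**Step 5: every arm changes by 1 SD at every visit.**
- Change unrelated to baseline: the joint test rejects 3% to 6.3%, the LS mean test more than 99%.
- r = 0.7, ρ = 0.8: the joint test rejects 71.6%, against 71.2% with no change. The Monte Carlo standard error of each figure is about √(0.714 × 0.286/2000) = 1.0 percentage point, so the two agree. The LS mean test rejects 100%.
- The single F tests reject 4.4% to 5.8% in both settings.

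At N=120 the pattern is the same: the joint test rejects 95.3% with no change at r = 0.7, and 4.7% under a common change unrelated to baseline.

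**Step 6: the OLE.** This model was not simulated. It has intercept, visit, baseline and age group, so a joint test would again leave out the intercept. The rates above should not be carried over.

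**The case against.** The strongest reply is that the document already contains the right test. The shells fix what is printed. Their row sits directly under the LS mean and its CI, the OLE versions remove only the vehicle-comparison rows, and no table has a place for an overall model P value. The paragraph also states the correct null immediately after introducing the LS mean and CI, and that CI gives the same two-sided 5% decision. Section 6.1.3 makes secondary P values informational. All of this stands, and it limits the practical harm. It does not make the sentence correct: the Section 8 text and the shells still specify different tests, and the shell's own programming note refers back to Section 8.1 for the alternative covariance structures.

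Second, the SAP does not say which overall P value it means. This also stands. Excess rejection occurs only under the joint-test and covariance readings. The covariance reading is an unlikely one for a sentence about mean change. The single F tests keep their size and fail only by missing a common change. The two faults of the joint test also need different conditions: excess rejection needs baseline to predict change, while near-5% rejection under a common change needs it not to.

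Third, normal scores are a rough stand-in, above all for the IGA, a five-point scale with entry restricted to grades 3 and 4.

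A reader might infer that the reported P value will be small almost regardless of whether patients changed. The figures do not support that: at correlation 0.85 to 0.9 the joint test rejects only 25% to 32%, and the shells do not call for it. A reader might also take every continuous efficacy endpoint to be affected. Ectropion and EQ-5D are summarised descriptively only (Sections 8.3.1 and 8.3.2), and DLQI/cDLQI has no OLE model.

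**Conclusion.** The point holds as an error of specification and a conflict between text and shell. Under none of the readings considered does an overall MMRM P value test that change from baseline is 0. The result that does not depend on assumed values is algebraic: the candidate mean tests exclude the intercept and so cannot detect a change common to all arms and visits, and the covariance test does not concern means at all. The size of the joint test's excess rejection, about 25% to 98% at N=65, depends on the assumed correlation (0.9 to 0.5), normal scores and complete data, and describes the three-arm double-blind model only.

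The harm is conditional on Section 8 being followed instead of the shell. It would matter most for the four endpoints modelled in the OLE. The active-versus-vehicle LS mean differences, which have their own null and P values, the within-arm CIs and the logistic analysis of the primary endpoint are not affected. The sentence should be corrected, but it does not threaten the trial's main comparison.

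**What to change.** In Sections 8.1.1, 8.2.1, 8.2.2, 8.2.3 and 8.2.4, replace the sentence with:

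> For each treatment group and visit (each visit in the OLE, where modelled), the LS mean change from baseline will be tested against 0 with a two-sided t test from the MMRM using Kenward-Roger degrees of freedom.

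Report no overall model P value for this hypothesis. The shells need no change, since this is what their row already implies.

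The cost is one sentence in five places. The test is standard output of the same model fit and needs no new data. The SAP states that it is filed before any unblinded analysis, so the edit can be made at that stage without touching any treatment comparison.

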8.2.2. Individual Score for Roughness

The amount of roughness of the skin overall will be measured on a 5-point scale at all clinic visits. The scoring is as follows in [Table 6](#).

Table 6: Roughness Scoring Definitions

Score	Definition
0	Clear: Smooth skin
1	Almost clear: Hardly palpable roughness
2	Mild: Mild roughness on palpation (fine sand paper-like)
3	Moderate: Moderate, coarse roughness (coarse sand paper-like)
4	Severe: Very coarse skin (broken cornflakes-like)

The change from baseline individual score for roughness will be analyzed using an MMRM. The MMRM model will include change from baseline in individual score for roughness as the dependent variable, treatment, study visit, treatment-by-visit interaction, and age group as fixed effects, subject as a random effect, and baseline individual score for roughness as a covariate. All post-baseline study visits will be included in the model; however, the primary comparison will be between the active trifarotene cream HE1 groups and vehicle at Day 90. An unstructured covariance matrix will be used to model the within-subject errors. The Kenward-Roger approximation will be used to estimate degrees of freedom. In case of convergence issues, other covariance structures will be explored including AR(1), CS, and VC with each model fit to find the covariance structure with the best fit. The fit statistics will be compared for all covariance structures; the structure with the smallest Akaike information criterion will be retained as the preferred model and noted in the resulting table. For the OLE period, the model will not include treatment or treatment-by-visit interaction since all subjects receive the same treatment in the OLE.

The LS mean change from baseline will be presented along with the associated 95% CI within each treatment group. The overall *P* value of the model will be presented to test the null hypothesis that the change from baseline to subsequent study visit is 0 with a 2-sided alternative considering a difference in either direction.

In comparing treatments (active trifarotene cream HE1 groups minus vehicle), LS mean differences in change from baseline will be presented along with associated 95% CIs and *P* values. The null hypothesis that the difference in change from baseline in active trifarotene cream HE1 groups minus control vehicle is 0 with a 2-sided alternative considering a difference in either direction.

The observed value and change from baseline in individual score for roughness will also be summarized descriptively by study visit and treatment group using descriptive statistics in addition to the above noted model for the Double-blind Period and OLE.

Additionally, the proportion of subjects who experience a 2-grade change from baseline to Day 90 in individual score for roughness will be summarized by treatment group and analyzed using a logistic regression model with treatment, baseline individual score for roughness, and age group as factors. The odds ratios and 95% CIs for the odds ratios will be presented. The difference in proportions between the active trifarotene cream HE1 groups and vehicle cream group, 95% CIs for the differences, and *P* values for the differences in treatment will also be presented.

The potential for heterogeneity of treatment effects will be assessed by testing treatment-by-factor interactions. The logistic regression model for the analysis will be expanded to include the treatment-by-age group interaction. In the event of quasi or complete separation, the logistic regression model will use Firth’s penalized maximum likelihood estimation.

